Identifiers: NCT03500146 Unique Protocol ID: 2016-248

Brief Title: Sexual Function Trial of Overactive Bladder: Medication Versus PTNS (STOMP)

**Document Date 8/22/2017
Uploaded 8/12/2020**

STOMP: Sexual function Trial of Overactive bladder: Medication versus PTNS

Research Plan

Specific aims:

Primary aim:

Aim 1: To determine if there is greater improvement in female sexual function as measured by the female sexual function index (FSFI) with percutaneous tibial nerve stimulation (PTNS) as compared to medical therapy (MT).

Hypothesis: The investigators expect that there will be a greater improvement in overall FSFI with PTNS as compared to MT.

Secondary aims:

Aim 2: To determine if improvement in female sexual function with percutaneous tibial nerve stimulation or medical therapy is correlated with improvement in urinary symptoms as measured by the OAB-q questionnaire.

Hypothesis: The investigators expect that improvement in urinary symptoms will be correlated with improvement in sexual function but that the difference in FSFI between groups will not be solely attributable to differences in urinary symptom improvement.

Aim 3: To determine if changes in sexual function are greater with beta agonist medications as compared to anticholinergic medications.

Hypothesis: The investigators expect that beta agonists will result in improved sexual function as compared to anticholinergics.

Aim 4: To determine if those patients with female sexual dysfunction as defined as an overall FSFI score below 26.5 have greater improvements than those without.

Hypothesis: The investigators expect that patients with female sexual dysfunction will have a greater improvement in FSFI than those without.

Research Strategy

Significance:

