The purpose of this study is to examine the comparative effectiveness of neuromodulation via percutaneous tibial nerve stimulation and medical therapy with anticholinergics or beta-agonists in improving female sexual function. Additionally this study will assess whether improvement in sexual function is correlated with improvement in urinary symptoms. Furthermore the effectiveness of anticholinergics as compared to beta agonists with respect to changes in sexual function will be examined. Lastly the investigators aim to determine if patients with female sexual dysfunction have greater improvements than those without, as this may open the

door to future studies using PTNS for the primary indication of female sexual dysfunction. Enhanced understanding of the effects of neuromodulation and medical therapy on sexual function may allow for improved patient selection and better outcomes which may lead to widespread use of neuromodulation for female sexual dysfunction.

Innovation:

While MT and PTNS have both been shown to improve female sexual function as compared to baseline as measured by the female sexual function index, there is a dearth of literature regarding their comparative effectiveness. A single study compared SNM to MT with sexual function examined only using the ICIQ OAB questionnaire which contains questions regarding sexual function but is not specific to sexual function and cannot tease out dysfunctions in specific domains. SNM is also more invasive than PTNS. Less is known about the effects of PTNS on sexual function and only a single underpowered study exists comparing PTNS to MT with respect to sexual function. Additionally there are conflicting results regarding whether the improvement in sexual function seen with PTNS and MT is associated with improvement in urinary function. If as hypothesized, sexual function improves to a greater extent with PTNS than with MT although both result in a similar improvement in urinary symptoms; it suggests that there may be additional mechanisms by which PTNS affects sexual function. Improved understanding of these effects may lead to clinical use of PTNS for FSD, a condition for which few treatments exist.

Approach:

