This will be a prospective multi-center cohort study comparing changes in sexual function in women undergoing PTNS or MT for OAB/UUI. Potential subjects will be adult women presenting to a urogynecology clinic for symptoms of overactive bladder such as urgency and UUI. Eligible subjects must report urinary urgency or urge incontinence and be recommended for treatment with medical therapy (with anticholinergic or beta agonist) or PTNS by the treating physician. Women meeting inclusion criteria will be asked to complete the validated OAB-q, FSFI, Beck Depression Inventory and a visual analog pain scale prior to therapy and then again after twelve weeks of therapy. Patients will also be specifically asked about the presence or absence of fecal incontinence and known side effects of therapy. Demographic data including age, comorbidities and menopausal status will be extracted from the medical record.

Women meeting inclusion/exclusion criteria will be prospectively enrolled.

- Women who are prescribed MT will be instructed on adherence to therapy for the twelve week duration of the trial. Therapy prescribed (anticholinergic versus beta agonist) will be based on shared decision-making between the patient and the treating physician.
- Women who are prescribed PTNS will undergo weekly 30 minute stimulation sessions for 12 weeks using a tibial nerve stimulator (Urgent® PC, Uroplasty, Minnetonka, MN, USA). The technique consists of stimulating the nerve by means of a 34 gauge needle electrode inserted approximately 2 inches cephalad and 1 inch posterior to the center of the ankle. The needle is inserted at a 60° angle pointing toward the head and advanced until approximately half of the needle is inserted into the leg. The lead wire is then connected to the stimulator and the surface electrode is placed on the inside of the arch of the foot of the treatment leg. The patient treatment level is identified by slowly increasing the current while observing the patient's foot for a motor response (usually toe flex, fan, or twitch) and asking the patient to report any sensations they feel (typically mild pulsing sensation). Once treatment level is identified, therapy mode is initiated and continued for 30 minutes.

Inclusion criteria:

- Female patients greater than 18 years of age

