- Symptomatology of urinary urgency or urge incontinence planning to undergo MT or PTNS. Patients must meet a threshold bother defined by a positive response and bother of "somewhat, quite a bit, a great deal, or a very great deal" to questions #2, #3 or #8 on the OAB-q regarding urinary urgency and urgency incontinence.

- Patients may have tried other medication for overactive bladder in the past but should be off therapy for at least one month
- Patients must be currently sexually active with sexual activity within the past month and plans to continue for the duration of the study. Sexual activity, as defined in the FSFI questionnaire, may include caressing, foreplay, masturbation, and vaginal intercourse.
- Patients must be willing and able to complete questionnaires in English

Exclusion criteria:

- Contraindications to PTNS (skin, orthopedic or anatomical limitation that could prevent placement of PTNS electrode, presence of pacemaker)
- Contraindications to both anticholinergic and beta agonist therapy
- Current symptomatic UTI within past week
- Pregnant or planning to become pregnant
- Prior treatment with SNM, PTNS, onabotulinum toxin A or two medications (stopped for reasons unrelated to side effects)
- Diagnosed or suspected interstitial cystitis/painful bladder syndrome
- Diagnosis of neurogenic bladder
- Prolapse greater than Stage 2, pessary use or planned surgery for pelvic floor disorder during the study
- Planned simultaneous treatment with both PTNS and MT

Statistical analysis and Sample Size Calculation:

The proposed study will consist of two treatment groups (MT versus PTNS). The decision to conduct a two-arm prospective cohort as compared to a three-arm randomized controlled trial was based on assessment of feasibility. The primary endpoint of the study is improvement in overall FSFI score which the investigators hypothesize to be greater in the PTNS group.

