Sample size calculations were conducted using <http://clincalc.com/stats/samplesize.aspx> with the primary endpoint of FSFI assessed as a continuous variable. Group sample sizes of 63 per group (total 126 patients) will be necessary to detect a clinically relevant difference of 5 points in FSFI assuming standard deviation of 10 [13] and achieve a power of 80%, $\alpha=0.05$. By incorporating a 10% loss to follow-up rate, the investigators propose to recruit 70 patients per group, with a total of 140 patients. Because approximately 45% of patients with OAB will have FSD as determined by an FSFI score below 26.5, the investigators aim to include up to 312 patients in the study.

Initial statistical analysis will provide descriptive statistics on the demographic and clinical characteristics of the study participants using means, standard deviations, median and range for continuous variables and frequencies and percentages for categorical variables. To examine potential differences between the study groups at baseline, descriptive statistics will be obtained for each group and compared statistically using two-sample t-tests, nonparametric rank tests, chi-square and Fisher's exact test as appropriate. All outcome variables will be summarized using similar methods for initial data and 12-week follow-up.

Wilcoxon signed rank test will be used to assess changes in FSFI before and after treatment as the investigators expect the quantitative data from this to have a skewed distribution given the nature of the FSFI score. A subgroup analysis will be performed to determine if those patients with female sexual dysfunction as defined as an overall FSFI score below 26.5 have greater improvements in FSFI than those without. Mann-Whitney U test will be used to compare FSFI scores between the MT and PTNS groups again because of the skewed nature of the distribution. Spearman's correlation will be used to assess for correlation between urinary symptoms, and FSFI.

We will analyze both intention to treat (ITT) and per protocol (treated) samples for the primary outcome. To handle missing data, the investigators will employ multiple imputation models for the ITT analyses. The investigators will also examine the difference between patients who complete the study and those who were

lost to follow-up based on baseline demographic and clinical characteristics to evaluate type of missingness, adherence to therapy and limits to generalizability.

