We will conduct secondary/advanced analyses by specifying multivariate regression models of the primary outcome measures in order to estimate treatment differences adjusted by potential confounders. Specifically, multiple linear regression analyses will be used to adjust the post-treatment change scores for baseline values of the outcome variables as well as age, OAB-q and BMI. These models will be estimated using cluster options (Intercooled Stata, command cluster) to account for the correlations between patients who are treated in the same hospital/site.

A planned interim analysis will be conducted comparing patients receiving anticholinergics and those receiving beta agonists. This will be conducted once 63 patients receiving anticholinergics and 63 receiving beta agonists have completed the study. This will address Aim 3. A Mann-Whitney U test will be used to compare FSFI between patients receiving anticholinergics and beta agonists.

Data Collection and Transmission:

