Visual analog pain scale		X	X
FSFI		X	X

Follow up medical history			X
---------------------------	--	--	---

Potential Difficulties:

There may be difficulty in recruiting patients for this study as patients may not be sexually active or may think discussion of sexual function is taboo. In order to account for this, the study will be a multi-center trial organized through the American Urogynecological Society-Society of Gynecologic Surgeons Fellows Pelvic Research Network (AUGS-SGS FPRN) to have a greater population from which to recruit patients. This project was submitted and accepted for presentation at the AUGS-SGS FPRN project proposal meeting. The FPRN is a fellow-run multi-center research network created to enable fellows to conduct multi-center pelvic floor research projects. At the meeting, which was held during the annual AUGS meeting on September 28th 2016, multiple sites demonstrated interest and the network decided to undertake the project. All participants within the Fellows Pelvic Research Network are based at academic institutions with sufficient volume to support fellowship training in Female Pelvic Medicine and Reconstructive Surgery. The investigators are currently planning to recruit patients at MedStar Franklin Square Medical Center, Indiana University, Oklahoma University and UT Southwestern Medical Center in addition to MedStar Washington Hospital Center.

There may also be difficulty in adherence to treatment as patients may develop side effects to medical therapy or difficulty in adhering to the weekly schedule for PTNS causing them to stop treatment, these patients will be analyzed with intent to treat analysis. Patients who choose to stop therapy will be asked to fill out completion questionnaires at the time they inform their physician that they would like to stop treatment.

Patients who undergo PTNS often are MT failures thus they may have higher OAB baseline scores and possibly more sexual dysfunction, as patients and their physicians choose treatment in this study, this cannot be controlled for. However, there are many patients in our practice who choose to pursue PTNS as initial treatment as well as patients who choose to pursue MT with a second medication after trying a first. By excluding patients who have failed treatment with two prior medications (stopped unrelated to side effects), the investigators aim to minimize differences between groups.

Budget:

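### Aim 4 compares FSFI change between women split at 26.5 on the score that starts the change, so regression to the mean can produce the hypothesised result without any difference in benefit

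*Combined protocol and SAP*

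**What the plan says.** Specific aims, Aim 4, gives a directional hypothesis: "The investigators expect that patients with female sexual dysfunction will have a greater improvement in FSFI than those without". Statistical analysis and Sample Size Calculation turns this into a subgroup comparison: "A subgroup analysis will be performed to determine if those patients with female sexual dysfunction as defined as an overall FSFI score below 26.5" improve more than those without. It names no test for that comparison and does not say which FSFI measurement defines the subgroup.

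Under Approach, questionnaires including FSFI are completed "prior to therapy and then again after twelve weeks of therapy". The Study Timeline table agrees, showing FSFI at Day 0 and at 12 weeks only. Potential Difficulties adds that women who stop therapy complete the final questionnaires when they stop.

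Both cohorts are treated: "The proposed study will consist of two treatment groups (MT versus PTNS"). Baseline FSFI does enter a regression, but its stated purpose is to fit "multivariate regression models of the primary outcome measures in order to estimate treatment differences adjusted by potential confounders". The plan does not assign that model to Aim 4. Regression to the mean is not mentioned anywhere.

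Significance gives the intended use of Aim 4: the result may open the "door to future studies using PTNS for the primary indication of female sexual dysfunction".

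**The concern.** A woman's pre-treatment FSFI is partly a lasting level and partly how she happened to score that day. Selecting women below 26.5 picks out more who scored low by chance, and the remainder include more who scored high by chance. On retest both groups drift towards the middle, so the low group gains relative to the high group. The change score then counts that drift as improvement.

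The drift runs the way the hypothesis predicts. A significant Aim 4 result in that direction therefore could not, by itself, be attributed to greater benefit in women with sexual dysfunction. With no untreated group, the data offer no estimate of the drift to subtract. A rank test deals with skew but not with this bias. At stake is whether a positive Aim 4 can support moving PTNS towards sexual dysfunction as an indication.

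**Working it through.** **The plan's own figures.** With a 5-point difference, SD 10, two-sided 0.05 and 80% power, n = 2 × 2.80² × 10² / 5² = 62.7, or 63 per group and 126 in total. Allowing 10% loss, 63 / 0.9 = 70 per group. For the larger enrolment, 70 / 0.45 = 155.6, rounded up to 156 per group, or 312. All of these reproduce. Completers used below are 126, and 312 × 0.9 = 281.

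**Direction.** Let b = r × SD(12 weeks) / SD(baseline). With no difference in benefit, expected change falls by (1 − b) points for each extra point of baseline FSFI. The low group therefore gains relative to the high group whenever b is below 1. With equal SDs, that is any r below 1.

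**Size.** Inputs from the plan are 45% below 26.5 and SD 10. Assumptions are that SD 10 is of the score, SDs are equal at both times, and scores are normal.

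- The cut at 45% is z = −0.1257, where the normal density is 0.3958.
- Distance between the two group means at baseline: 0.3958/0.45 + 0.3958/0.55 = 1.599 SD, or 15.99 points.
- Spurious difference in change: 15.99 × (1 − r).
- It equals the plan's clinically relevant 5 points at r = 1 − 5/15.99 = 0.687.

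If SD 10 is instead the SD of change, the score SD is 10/√(2(1 − r)) and the gap is 15.99 × √((1 − r)/2).

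**False support for the hypothesis.** The plan names no test, so a two-sided Mann-Whitney test on change at 0.05 is assumed. The last two columns show how often it was significant in the hypothesised direction over 10,000 simulated trials with no true difference and score SD 10.

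| r | Gap, SD 10 of score | Gap, SD 10 of change | 126 completers | 281 completers |
|---|---|---|---|---|
| 0.7 | 4.8 | 6.2 | 94% | 100% |
| 0.8 | 3.2 | 5.1 | 80% | 99% |
| 0.9 | 1.6 | 3.6 | 50% | 84% |
| 0.95 | 0.8 | 2.5 | 27% | 54% |

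Significance in the opposite direction occurred in 0.1% of trials or fewer. The plan expects skew. With an assumed left-skewed score (1,500 trials) the rates with 126 completers were 96%, 84%, 58% and 31%.

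**Precision of an interaction test.** With equal arms, FSD dichotomised, 45% FSD in each arm, score SD 10 and site clustering ignored, the detectable baseline-adjusted interaction at 80% power is 2.80 × 10 × √(1 − r²) × √(4/(0.45N) + 4/(0.55N)).

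- N = 281: 4.8 points at r = 0.7 and 4.0 at r = 0.8.
- N = 126: 7.2 and 6.0 points.

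In simulated trials with no effect, this interaction test rejected in about 4% to 6%, including when the PTNS arm started 4 points lower.

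**The PTNS-versus-MT difference within FSD.** Potential Difficulties expects PTNS patients possibly to have more sexual dysfunction. Suppose they are 4 points lower at both times and treatment has no effect. The baseline-adjusted difference is then biased by −4 × (1 − r): −1.2 points at r = 0.7 and −0.8 at r = 0.8. With 281 completers it rejects in about 17% and 12% of trials. It holds its nominal 5% only if follow-up scores in both arms lie on one common regression line.

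**The case against.** The strongest reply is that only the direction is supported, and that conditionally. If treatment widened the spread of scores enough (SD ratio above 1.25 at r = 0.8, or above 1.11 at r = 0.9), the artefact would vanish or reverse. This stands, so the bias should not be called unconditional.

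The size is also uncertain. The documents give no r, name no test for Aim 4, and do not say whether SD 10 is of the score or of change. A reader might infer that the artefact is sure to reach 5 points, or that the rejection rates describe the plan's own test. Neither follows: with score SD 10 the gap reaches 5 points only if r is about 0.69 or lower, and the test is assumed. False significance does not need 5 points, however, and at r = 0.95 the rates are still far above nominal.

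A third reply is that Aim 4 asks only who improves more, which the raw contrast answers descriptively, and that no before-after change in this study can be attributed to treatment. This is fair as far as description goes. But the plan states a directional hypothesis and an onward use, and both read the contrast as greater benefit.

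Finally, the cut is never expressly called a baseline score. The schedule leaves no other pre-treatment FSFI, so the reading is safe, but it is a reading.

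**Conclusion.** The concern holds in conditional form. Provided r × SD(12 weeks)/SD(baseline) is below 1, regression to the mean moves the Aim 4 contrast towards its own hypothesis, and nothing in the plan assigned to Aim 4 corrects for it. The spurious gap of about 16 × (1 − r) points is illustrative. It rests on score SD 10, equal SDs, normal scores and 45% FSD. For r above 0.5 it is larger if SD 10 is of change.

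A reader might go on to infer that the primary PTNS-versus-MT result is compromised. This mechanism does not reach it, because the primary comparison does not sort women by their starting FSFI. Nor do the documents say that the larger enrolment was sized for Aim 4. The plan says only that "the investigators aim to include up to 312 patients in the study". That this provides 70 women with FSD per group is an inference from the arithmetic.

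This is a defect in a secondary aim. It should be fixed before analysis.

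**What to change.** **Minimum.** State that FSD is defined on the Day 0 FSFI. Report change by FSD status descriptively, label it as affected by regression to the mean, and draw no conclusion from it that women with FSD benefit more.

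**If inference is wanted.** Add a treatment-by-baseline-FSFI interaction, with baseline continuous, to the planned regression. State that it asks whether the PTNS-versus-MT difference depends on baseline function, which is narrower than Aim 4. Label it exploratory and observational, since the plan concedes of baseline differences between the groups that "as patients and their physicians choose treatment in this study, this cannot be controlled for".

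Simply adding baseline FSFI to the Aim 4 comparison is not a full answer. In simulation it brings rejection back to about 4% to 6%, but the FSD term then no longer measures greater improvement.

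**If the PTNS-versus-MT difference within FSD is shown.** Keep it descriptive. Note that a lasting baseline difference between arms biases the adjusted estimate by about that difference × (1 − r).

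**Cost.** One analysis paragraph and one interpretation sentence, with no new data. The downsides are a narrower question, remaining confounding by treatment choice, and limited precision: only interactions of about 4 to 5 points with 281 completers, or 6 to 7 with 126, are detectable at r of 0.7 to 0.8.

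### Treatment is chosen and baseline imbalance is expected, yet no Aim 1 analysis is named primary: the lead PTNS-versus-MT test is unadjusted, and the adjusted model is ranked secondary and omits confounders the study collects

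*Combined protocol and SAP*

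**What the plan says.** The Approach section describes the design: "This will be a prospective multi-center cohort study comparing changes in sexual function in women undergoing PTNS or MT for OAB/UUI". Treatment follows the physician's recommendation and the patient's choice. Potential Difficulties says what this is likely to do: "Patients who undergo PTNS often are MT failures thus they may have higher OAB baseline scores and possibly more sexual dysfunction", and adds that "as patients and their physicians choose treatment in this study, this cannot be controlled for". The stated mitigation is an exclusion: "Prior treatment with SNM, PTNS, onabotulinum toxin A or two medications (stopped for reasons unrelated to side effects". Women with one failed drug remain eligible.

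Statistical analysis and Sample Size Calculation defines the endpoint: "The primary endpoint of the study is improvement in overall FSFI score". It then gives the between-group test, "Mann-Whitney U test will be used to compare FSFI scores between the MT and PTNS groups", with no covariates and without calling it primary. Intention-to-treat (ITT) and per-protocol samples are both to be analysed for the primary outcome, neither ranked first, with multiple imputation for ITT.

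Later in the same section, under analyses labelled secondary, multiple linear regression adjusts FSFI change for baseline FSFI, age, OAB-q and BMI, with clustering by hospital or site. The time point of OAB-q is not spelled out. Potential Difficulties lists five sites as currently planned.

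**The concern.** An unadjusted comparison in a chosen-treatment cohort cannot separate the effect of treatment from the effect of who chose it. The protocol expects the arms to differ, so this is not a remote risk.

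Three features of the plan leave the problem open.

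- **Ranking.** No analysis is named primary, and the adjusted one is labelled secondary. If the two disagree, either could be presented as the answer to Aim 1.
- **Outcome wording.** The endpoint is improvement, but the test is worded as a comparison of scores. A test of 12-week scores would carry any baseline gap straight into the result.
- **Covariates.** The adjusted model omits variables that the protocol itself says affect sexual function, and omits the route by which it expects women to be selected into PTNS.

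**Working it through.** **1. The plan's own figure.** Inputs from the sample size paragraph: difference 5, SD 10, power 80%, alpha 0.05 (two-sided assumed). n per arm = 2 × (1.960 + 0.842)² × 10² / 5² = 62.8, so 63. With 10% loss, 63 / 0.9 = 70. Both stated figures reproduce. The calculation assumes an unbiased comparison of two means.

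**2. Covariates, side by side.**

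| Variable | Where it appears | In the planned regression? |
|---|---|---|
| Baseline FSFI | Approach | Yes |
| OAB-q (bladder symptoms) | Significance (as a determinant), Approach | Yes |
| Age | Approach | Yes |
| BMI | Regression paragraph | Yes |
| Beck Depression Inventory | Significance (as a determinant), Approach | No |
| Pain scale | Significance (as a determinant), Approach | No |
| Fecal incontinence | Significance (bowel function), Approach | No |
| Comorbidities | Significance (as a determinant), Approach | No |
| Menopausal status | Approach | No |
| Prior OAB medication | Potential Difficulties (selection route), eligibility criteria | No |

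Prior medication can be adjusted for only if the arms overlap on it. Potential Difficulties says they do: "many patients in our practice who choose to pursue PTNS as initial treatment", and on the other side "patients who choose to pursue MT with a second medication after trying a first".

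**3. Illustration of the bias.** The documents give no baseline gap and no baseline-to-follow-up correlation. Assumed: PTNS 3 points lower at baseline, r = 0.5 or 0.7, normal data, no treatment effect. SD 10 and 63 per arm are the plan's.

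*Gap regresses* (12-week gap = r × 3):
- Bias of unadjusted change = 3 × (1 − r) = +1.5 or +0.9.
- SD of change = 10 × √(2(1 − r)) = 10.0 or 7.75. SE = SD × √(2/63) = 1.78 or 1.38.
- Normal-approximation false positives: 13% or 10%. Simulated Mann-Whitney on change (4,000 runs): 11.9% or 10.1%.
- Baseline-adjusted change: bias about 0, false positives about 5%.

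*Gap persists* (12-week gap = 3):
- Unadjusted change: bias 0, about 5%.
- Bias of baseline-adjusted change = −3 × (1 − r) = −1.5 or −0.9.
- Residual SD = 10 × √(1 − r²) = 8.66 or 7.14. SE = SD × √(2/63) = 1.54 or 1.27.
- False positives: 16% or 11%. Simulated: 16.0% or 10.6%.

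A Mann-Whitney on 12-week scores would be biased by −1.5 to −2.1 if the gap regresses and by −3.0 if it persists.

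**4. What the extra covariates buy.** Simulated with one composite confounder, assumed 0.6 SD apart between arms:
- If it explains half the gap, the bias in change (gap regresses) falls to about +0.74 or +0.48, with about 6% false positives. The bias in baseline-adjusted change (gap persists) falls to −0.84 or −0.51, with 8% or 7%.
- If it explains all of the gap, both biases vanish.
- If it explains none, no bias is removed, and power for 5 points falls by at most about 4 percentage points (0.607 to 0.564 in the worst case). That is for one composite, so it only indicates the cost of six covariates.

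**5. Sample size does not help.** At 312 less 10%, split equally (312 × 0.9 / 2 = 140 per arm), simulated false positives rise to 23% or 15% (change, gap regresses) and 29% or 17% (baseline-adjusted, gap persists).

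**6. Site clustering.** With five sites and t on 4 degrees of freedom, the critical value is 2.78 against 1.96. Across the assumed site sizes and intraclass correlations of 0 to 0.05, simulated false positives are about 5% to 8%, near nominal. The cost is power. With 126 patients, a 0.5 SD effect and covariates that explain nothing, power is about 54% to 62% with cluster errors, against about 77% with ordinary errors.

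**The case against.** The strongest reply is that the imbalances the protocol names, bladder symptoms and sexual dysfunction, are already in the planned regression. The plan also compares the arms at baseline and restricts prior treatment failures. On this view only a label and a longer covariate list are missing. Much of that stands. A reader might infer that the plan ignores confounding or leaves Aim 1 wholly unadjusted; it does not. But the label decides which result leads, and the omitted variables are ones the protocol itself links to sexual function or to selection.

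A reader might also infer that clustering on five sites gives badly inflated false positives. Simulation gives 12% to 16% with normal critical values, but the documents nowhere propose those values. With t on 4 degrees of freedom the test is close to nominal. Site fixed effects with HC3 errors are not clearly better: false positives rise to 7% to 13% if the treatment effect varies between sites with an SD of 2 to 3 points, against 5% to 9% for cluster errors with t on 4 degrees of freedom. That choice is a trade-off and not a defect in the plan.

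Two further points stand. The plan chose rank tests because it expects skewed data, and the illustration assumes normality. Comorbidity, prior medication and the timing of the fecal incontinence question also need definition before they can serve as baseline covariates.

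**Conclusion.** The point holds as a matter of ranking and completeness. As written, the test most naturally read as the answer to Aim 1 is unadjusted in a cohort where imbalance is expected, while a better analysis sits below it with known determinants left out. That the Mann-Whitney is primary is an inference from the secondary label on the regression; the plan never says so.

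The size is illustrative: biases of about 0.9 to 1.5 points against a target difference of 5, under an assumed 3-point gap, r of 0.5 to 0.7, SD 10 and 63 per arm. A reader might infer that the bias favours PTNS, or that baseline adjustment removes it. The documents support neither. The Study Timeline puts the treatment decision at the intake visit, before the Day 0 FSFI, and nothing shows whether a gap would regress or persist. This should be fixed before analysis; it does not invalidate the study.

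**What to change.** Make the planned regression of FSFI change the single primary Aim 1 analysis, in the ITT sample, with the multiple imputation already planned.

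- **Covariates.** Keep baseline FSFI, OAB-q (stated as baseline), age and BMI. Add baseline Beck Depression score, baseline pain score, baseline fecal incontinence, menopausal status, a defined comorbidity variable, and prior OAB medication (none, or one or more).
- **Sensitivity analysis.** Report the same model without baseline FSFI, because baseline adjustment can itself bias the result if the gap is stable. Treat disagreement as a limit on the conclusion, and do not claim that the two bracket the truth.
- **Unadjusted support.** Run the Mann-Whitney on change.
- **Sites.** Keep clustering, state that it uses t on (sites − 1) degrees of freedom, and note the loss of power with about five sites. Site fixed effects are an optional sensitivity analysis.
- **Reporting.** State that unmeasured confounding remains.

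The cost is SAP wording, some analysis time and three data definitions (comorbidity, prior medication, the baseline time point for fecal incontinence). The downsides are six added covariates, a small loss of power if they explain nothing, and reliance on a linear model for data expected to be skewed.
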